7. The subject will be asked to give subjective ratings post lens settling

- a. Comfort (0-10 scale) and comments
- b. [REDACTED]
- c. [REDACTED]
- d. [REDACTED]

8. [REDACTED]

[REDACTED]

- [REDACTED]
- [REDACTED]
9. Monocular lens fit will be assessed and graded according to the CVI grading scales (Appendix 2). Lens fit will be video recorded in the event of poor fit.
 - a. Corneal coverage at all times (y/n)
 - b. Lens centration (optimal /slightly decentered, <0.5mm /extremely decentered >0.5mm, NTSI)
 - c. [REDACTED]
 - d. Post-blink movement (mm)
 - e. Primary gaze lag (mm)
 - f. Upgaze lens lag (mm)
 - g. Lens push-up tightness (%)
 - h. Overall lens fit acceptance (0-4 scale, and yes/no) and investigator reason, if unacceptable.
 - i. Overall lens fit impression (-2 to 2 scale)

10. The subject will be encouraged to wear the study lenses as much as they normally do with their habitual lenses and for a minimal of 5 days/week.

11. The subject will be instructed to discard study lenses at home nightly but to keep lenses with problem to return to the site.

12. The subject will be given enough contact lenses to wear until the next study visit.

13. The subject will be discharged and reminded to return for the one week visit of the first pair.

7.3.2 Visit 2: Follow-up Pair #1/Dispensing Pair 2

*Subjects will be asked to wear lenses for **at least 2 hours** prior to the visit appointment.*

Subjects who attend without lenses in situ for at least two hours will be rescheduled.

The following procedures will be performed (any ocular measurement procedures outlined below will be carried out on each eye):

[REDACTED]

- [REDACTED]
- [REDACTED]
- [REDACTED]
- [REDACTED]
- [REDACTED]

- Comfort at insertion, during the day, end of the day and overall comfort since the last visit (0-10 scale)

- [REDACTED]

2. [REDACTED]

- [REDACTED]
- [REDACTED]
- [REDACTED]
- [REDACTED]

[REDACTED]

4. [REDACTED]

- [REDACTED]
- [REDACTED] type
- [REDACTED]
- [REDACTED]

5. Monocular lens fit will then be assessed and graded according to CVI grading scales (Appendix 2).

- a. Corneal coverage at all times (y/n)
- b. Lens centration (optimal /slightly decentered, <0.5mm /extremely decentered >0.5mm, NTSI)
- [REDACTED]
- d. Post-blink movement (mm)
- e. Primary gaze lag (mm)
- f. Upgaze lens lag (mm)
- g. Lens push-up tightness (%)
- h. Overall lens fit acceptance (0-4 scale, and yes/no) and investigator reason, if unacceptable.

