10.1 Sample size

Approximately 70 subjects will be enrolled with a goal that approximately 50 will be completed. Based on historical clinical data a sample size of 50 completing subjects is sufficient to detect a mean difference of 0.5 (0 – 10) in subjective ratings assuming $\alpha=0.05$ and a power of 80% (Table 3).

Table 3: Sample Size Calculations

Mean individual difference in score	Mean individual standard deviation	Sample size, Power 80% (p = 0.05)
0.5	1.2	48

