10.2 Statistical analysis

Summary statistics will be produced (e.g. mean, standard deviation). Paired t test will be used to compare slit lamp biomicroscopy, lens fit and subjective scores between study lens types. Repeated Measures Analysis of Variance (ANOVA) or paired analysis will be used to compare the variables between study visits. The critical alpha level for statistical significance will be set at $p \leq 0.05$, with adjustment for multiple comparisons.

All participants who were evaluated will be used in the analysis. In the event of missing data, individual data points will be excluded in the analysis and not extrapolated from the collected data.

11 Data Quality Assurance

[REDACTED]

[REDACTED]

[REDACTED]

[REDACTED]

- [REDACTED]

- [REDACTED]

[REDACTED]

[REDACTED]

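### Does the paired t-test on the -2 to 2 lens fit impression miss a lens that fits worse in both directions?

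*Combined protocol and SAP*

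**What the plan says.** Section 10.2 names a single between-lens test for all fit items: "Paired t test will be used to compare slit lamp biomicroscopy, lens fit and subjective scores between study lens types". It also plans summary statistics, giving the mean and standard deviation as examples, and sets significance at 0.05 "with adjustment for multiple comparisons".

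Section 7.3.1 lists the fit items, and 7.3.2 repeats them at follow-up. Among them are "Overall lens fit impression (-2 to 2 scale") and, at the same assessment, "Overall lens fit acceptance (0-4 scale, and yes/no) and investigator reason, if unacceptable". The list also has corneal coverage as yes/no, centration in three steps starting from well centred, three measurements in millimetres, and push-up tightness in per cent. One further item is redacted.

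The anchors of the scales are elsewhere: "Monocular lens fit will be assessed and graded according to the CVI grading scales (Appendix 2"). The content of that appendix is not in the public text, so the meaning of -2, 0 and 2 cannot be read there.

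Section 10.1 bases the sample size on subjective ratings, not on fit: "a sample size of 50 completing subjects is sufficient to detect a mean difference of 0.5" on the 0-10 scale.

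**The concern.** A scale that runs symmetrically from -2 to 2 suggests that 0 is the target and that the two signs mark opposite kinds of misfit. On such a scale the mean measures direction, not quality. Suppose one lens sits off the target more often than the other, about equally in both directions. Its mean stays near 0, the paired t-test on the signed score sees no difference, and more subjects do not help. A reader might then take a non-significant result as evidence that the lenses fit equally well. Because 10.2 describes no comparison of distance from the target, it seems to leave a real difference in fit untested.

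**Working it through.** **1. The plan's own figure.** Section 10.1 (Table 3) gives a difference of 0.5, an SD of 1.2, two-sided alpha of 0.05 (assumed two-sided) and 80% power. The normal approximation gives (1.2 × (1.960 + 0.842) / 0.5)² = 45.2, so 46. With the noncentral t the answer is 48, with power of 80.7% at 48 and 82.3% at 50. The stated 48 reproduces. The fit impression plays no part in it.

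**2. Is the cancellation real?** Yes, if 0 is the optimum. The documents give no score distribution, so every rate here is assumed: one value per subject, n = 50, lenses independent within subject, and comparator 5/90/5% at -1/0/+1. Let the other lens be 20/60/20%.

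- Signed score: mean difference = (0.20 - 0.20) - (0.05 - 0.05) = 0. Power equals alpha, about 5%.
- Distance from 0: mean difference = 0.40 - 0.10 = 0.30; variance = 0.40 × 0.60 + 0.10 × 0.90 = 0.33; noncentrality = 0.30 × √50 / √0.33 = 3.69. Against a critical t of 2.01, power is about Φ(1.68) = 95%.

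**3. Does the signed test do its own job?** Under the null, with both lenses at 5/90/5%, it rejects in about 4.3% of simulated trials, so type I error is sound. For a one-directional shift (0/80/20%):

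- Signed: 0.20 × √50 / √(0.16 + 0.10) = 2.77, power about 78% (79% simulated).
- Distance: 0.10 × √50 / √(0.16 + 0.09) = 1.41, power about 28% (27% simulated).

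If the lenses err in opposite directions (5/65/30% against 30/65/5%), the signed test has 99.6% power and the distance test 5%. Each test is blind where the other sees. The signed test is the right one for a shift in direction.

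**4. What else in 10.2 would see two-way misfit?** The 0-4 acceptance grade, yes/no acceptance, degree of decentration and corneal coverage carry no sign that can cancel, and all are fit items under the same sentence. The SD is also planned. At 20/60/20% against 5/90/5%, the SDs are √0.40 = 0.63 and √0.10 = 0.32, a twofold gap printed beside the means.

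**5. What would the extra test add?** The table credits only the 0-4 acceptance grade and assumes it loses one point for a given share of off-target fits. Each entry is the power of signed plus acceptance (0.025 each), then with distance added (0.0167 each), from 40,000 simulated trials.

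| Lens with more misfit | all registered | 75% | 50% | 25% |
|---|---|---|---|---|
| 20/60/20% | 91 to 88% | 76 to 89% | 53 to 88% | 24 to 88% |
| 15/70/15% | 62 to 53% | 45 to 56% | 29 to 55% | 13 to 54% |
| 10/80/10% | 21 to 15% | 16 to 17% | 11 to 17% | 6 to 15% |

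For the one-directional 0/80/20% case, adding distance costs power: from 79% (signed alone at 0.05) to 70% (signed and distance at 0.025 each), or from 70% to about 61% when acceptance is also in the family.

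The added test therefore gains much only when misfit rises threefold or more, roughly equally both ways, and acceptance overlooks a good part of it. It loses when acceptance registers every misfit or the shift is in one direction. When misfit only doubles, power is at most 21% either way. Decentration, coverage and yes/no acceptance get no credit here, and counting them could narrow the gains.

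**The case for a change.** The strongest case for a change is that the cancellation does not depend on the assumed rates. If 0 is the optimum and misfit is symmetric, the signed test has power equal to alpha at any sample size. Exact symmetry is not needed either. With a comparator at 10/80/10% and misfit rising to 50%, split 22/28 or 20/30, signed power is only 8-18% against 90-93% for distance. The documents do not say how closely acceptance follows impression, and the addition would cost one line of analysis text.

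The algebra stands. What does not follow is that the plan is wrong. The premise rests on an appendix that the public text does not show: if the scale runs from worst to best, or if acceptance already grades every departure from the target, nothing is missing. The documents give no reason to expect two-way misfit, and Table 1 shows the same base curve (8.6 mm) and diameter (14.1 mm) for both lenses. Nor does the visible text plan to conclude equal fit from a non-significant result, so that misreading would be a fault in reporting and not in the design.

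**Conclusion.** The concern does not hold as an error. The paired t-test on the signed impression is a valid test of mean direction, holds its type I error, and is the better test when one lens shifts fit one way (79% against 27% in the example). Misfit without direction is covered by other fit items under the same analysis and shows in the planned SDs. The comparison behind the sample size is unaffected, and its figure of 48 reproduces.

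What remains is an optional extra analysis of one item outside the powered comparison. Its effect runs from a gain of 64 points (24 to 88%) to a loss of 9 (79 to 70%, or 62 to 53%), depending on rates and an acceptance-impression link that the documents do not give. Reasonable statisticians could choose either way. The power figures assume that 0 is the optimum, scores of -1, 0 and +1, one value per subject, 50 completers and an equal split of alpha; the two eyes of a subject were not modelled.

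### Section 10.2 assigns a paired t test to all of lens fit, but three lens-fit items are yes/no or categorical and need a named paired categorical method (minor)

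*Combined protocol and SAP*

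**What the plan says.** Section 10.2 of the combined protocol and SAP names a single test for comparing the two lenses: "Paired t test will be used to compare slit lamp biomicroscopy, lens fit and subjective scores between study lens types". Repeated measures ANOVA, or an unspecified paired analysis, is reserved for comparisons between visits. No method for binary or categorical data appears in the visible text. The same section sets the significance level at 0.05 "with adjustment for multiple comparisons", without naming the adjustment or the family of tests.

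The lens-fit items are listed in section 7.3.1 (Dispensing Pair #1, step 9) and again in 7.3.2 (step 5). Some are measurements, for example "Post-blink movement (mm". Three are not, or not wholly:

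- Step 9a: "Corneal coverage at all times (y/n".
- Step 9b: "Lens centration (optimal /slightly decentered, <0.5mm /extremely decentered >0.5mm, NTSI".
- Step 9h: "Overall lens fit acceptance (0-4 scale, and yes/no) and investigator reason, if unacceptable".

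**The concern.** A paired t test suits the mm, percentage and graded items well enough. It fits a paired yes/no item poorly, because only the subjects who differ between lenses carry information. Coverage and acceptability may well be 'yes' on both lenses for almost everyone, so few subjects may differ. That is an expectation; the documents give no rate.

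If nobody differs, the planned statistic cannot be computed, and its interval collapses to a point and claims a certainty that 50 subjects cannot give. If a handful differ, the normal approximation behind the t test is weak. The NTSI code, if it is a direction (an assumption, since the text does not expand it), has no mean difference to test.

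At stake are the p-values and intervals reported for these items. There is also the risk that the analyst must pick a method after seeing the data.

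**Working it through.** **Inputs.** From section 10.1 and Table 3: 50 completing subjects, difference 0.5, SD 1.2, alpha 0.05, power 80%. Sidedness is not stated; two-sided is assumed because it reproduces the stated number. The rates at which subjects differ between lenses are assumptions, shown as a range.

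**1. The plan's own figure.** A two-sided paired t test with the noncentral t distribution needs n = 48 (power 80.7%; 82.3% at n = 50). The normal approximation gives (1.2 × (1.960 + 0.842) / 0.5)² = 45.2, so 46. Table 3's 48 reproduces. It concerns the 0-10 ratings only.

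**2. The t test on a yes/no item.** Code each subject +1, −1 or 0. Let b and c be the numbers differing in each direction. Then

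mean d = (b − c)/n; s² = [(b + c) − n d²]/(n − 1); t = d/(s/√n), with 49 df at n = 50.

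The exact McNemar p-value for a one-way split of b to 0 is 2 × 0.5^b, capped at 1.

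- 0-0: d = 0 and s = 0, so t = 0/0 and the interval is [0, 0]. Exact p = 1. A score interval for the paired difference is ± z²/(n + z²) = ± 3.84/53.84, about −7% to +7%.
- 4-0: d = 0.08; s² = (4 − 0.32)/49 = 0.0751; SE = 0.0388; t = 2.064; p = 0.044. Exact p = 2 × 0.5⁴ = 0.125.
- 5-0: d = 0.10; s² = (5 − 0.5)/49 = 0.0918; SE = 0.0429; t = 2.333; p = 0.024. Exact p = 0.063.
- 6-0: t p = 0.013; exact p = 0.031.

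Lens fit is graded per eye and the unit of analysis is not stated. Treating 100 eyes as independent gives 0.0449 for 4-0, so the contrast does not depend on this.

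**3. Chance that nobody differs,** (1 − q)^50: 0.99^50 = 61%; 0.98^50 = 36%; 0.95^50 = 8%.

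**4. Overall type I error of the t test** at nominal 0.05, n = 50, equal lenses, averaged over the number of differing subjects:

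| Assumed differing rate | t test | exact McNemar |
|---|---|---|
| 2% | 0.002 | 0.000 |
| 4% | 0.014 | 0.0004 |
| 10% | 0.047 | 0.009 |
| 20% | 0.043 | 0.022 |
| 30% | 0.047 | 0.028 |

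At 1% the t test's size is 0.0002.

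**5. Effect of a multiplicity adjustment.** Smallest one-way split called significant under Bonferroni:

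| Tests | t test | exact McNemar |
|---|---|---|
| 1 | 4-0 | 6-0 |
| 2 | 5-0 | 7-0 |
| 3 | 6-0 | 7-0 |
| 9 | 8-0 | 9-0 |

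**6. Checking the remedy.** Test and interval must agree. For 4-0 a score interval for the paired difference runs from 0.003 to 0.188 and excludes zero, beside an exact p of 0.125. An exact interval for the share of differing subjects who favour one lens runs from 0.025^(1/4) = 0.398 to 1; it includes 0.5 and so agrees with the exact test. Mid-p McNemar gives 0.0625 for 4-0 and 0.031 for 5-0. For every count of differing subjects from 1 to 20 except 4, its conditional rejection rate equals that of the t test (for example 6.25% at 5 and 7.0% at 8).

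**The case against.** The strongest reply has five parts.

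- **Multiplicity.** A reader might infer that the trial would declare a difference on a 4-to-0 split. The documents do not support that: section 10.2 promises adjustment, and 0.044 fails Bonferroni with only two tests (0.025). Under Holm or a false-discovery method it would depend on the other p-values. This stands. The disagreement between the tests moves to larger splits, but narrows.
- **Error rate.** A reader might infer that the t test inflates false positives. Overall it does not. It rejects 12.5% of the time when exactly four subjects differ, but never when one to three do, and 3.1% of the time at six. Much of the gap reflects the conservatism of the exact test. This stands.
- **Undefined result.** When nobody differs, the observed difference is zero and no conclusion changes. That is true of the p-value. It does not rescue a zero-width interval.
- **Wording.** The word 'scores' in section 10.2 might limit the t test to graded items: acceptance also has a 0-4 score and fit impression runs from −2 to 2. Summary statistics could then cover the counts. On that reading the yes/no items and centration have no named between-lens test, and the same edit is needed. Nothing says that NTSI codes would be averaged. The appendix with the fit grading scales is not shown, and that is not held against the plan.
- **Importance.** It is tempting to say that these items decide whether a fit claim stands. No fit claim, success criterion or primary fit endpoint is visible, and the objective and hypothesis text is redacted. The only powered outcome visible is the 0-10 rating.

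**Conclusion.** The point holds, and it is minor. The visible plan either applies a paired t test to items it does not suit or leaves them without a test. For the two yes/no items, the consequences are an uncomputable statistic and zero-width interval when nobody differs, and p-values below the exact ones when few differ.

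The probabilities of no differing subject rest on assumed rates of 1% to 5%, and the p-values on n = 50 with one value per subject. The point about NTSI rests on reading it as a direction. The powered 0-10 comparison and Table 3 are not affected.

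**What to change.** Amend section 10.2 as follows:

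- Limit the paired t test to numeric and graded items (mm, %, 0-10, 0-4, −2 to 2).
- For corneal coverage and yes/no acceptance, analyse one value per subject, and state how the two eyes are combined. Use the exact McNemar test with a matching exact interval for the paired comparison, or mid-p McNemar with a matching mid-p interval. Report the paired counts in every case; they matter most when few or no subjects differ.
- For the centration grade, use a paired ordinal test such as the Wilcoxon signed-rank test, or compare optimal with not optimal by McNemar. Only tabulate the NTSI code.
- Apply the same multiplicity adjustment to these items as to the rest.

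The cost is a few sentences, with no new data and no more subjects. The one downside is that the exact test is conservative and will call fewer sparse differences significant; the mid-p version eases this, at the price of conditional rejection rates close to those of the t test.

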11.2 Record keeping

Detailed records of all study visits will be made using the Case Report Forms (CRFs). All data recorded on forms will be in ink. Any corrections to the forms will be initialed and dated at the time they are modified.

11.3 Record retention

Following study completion, data will be available in electronic and/or paper format for audit, sponsor use, or subsequent analysis. The original clinical raw data (including completed CRFs and Informed Consent forms) will be retained according to guidelines set forth in the general work agreement with the site. The Sponsor will be notified and consulted if ever the files are to be destroyed. In the event that this implementation document is indicated for design verification and validation purposes, as indicated on the title page, all original raw data forms and completed CRF's will be forwarded to the sponsor at completion of the final report.

11.4 Data Entry / Data Management

Data will be entered into an electronic spreadsheet. Study staff will only be able to modify the data file via password entry. The investigators will be responsible for the data integrity, and complete data entry for each visit as well as the take home questionnaires. The investigator will send the data collected to the study sponsor within approximately 5 business days after the last subject completes the final visit.

11.5 Confidentiality

This study is confidential in nature. Details of confidentiality are covered within the Master Agreement signed between the sites and the sponsor.

All records will also be handled in accordance with HIPAA (1996) standards.

11.6 Publication

Publication conditions are laid out in the Master Agreement signed between the sites and the sponsor.

12 Study Costs

The sponsor will compensate the clinical site and the subjects for their time and participation in this voluntary study.

[REDACTED]

13 Appendices
